PROTOCOL TITLE: Examining the Effects of Juice Fasting

PRINCIPAL INVESTIGATOR:

[name], FACP

Executive Director

Osher Center for Integrative Medicine at Northwestern University

[name]

[name]

[contact] (Office)

[contact]

[name], PhD

Associate Professor of Preventive Medicine

Northwestern University, Feinberg School of Medicine

[name]

[name]

[contact] (Office)

[contact]

[name]

Post-Doctoral Fellow

Northwestern University, Feinberg School of Medicine

[name]

[name]

[contact] (Office)

[contact]

VERSION NUMBER:

1.4

VERSION DATE:

05-22-18

STUDY SUMMARY:

Investigational Agent(s) (Drugs or Devices)	N/A
ÎND / IDE / HDE #	N/A
Indicate Special Population(s)	☐ Children ☐ Children who are wards of the state ☐ Adults Unable to Consent ☐ Cognitively Impaired Adults ☐ Neonates of Uncertain Viability ☐ Pregnant Women ☐ Prisoners (or other detained/paroled individuals) ☐ Students/Employees
Sample Size	30
Funding Source	Osher Center for Integrative Medicine at Northwestern University
Indicate the type of consent to be obtained	 ☑Written ☐Verbal/Waiver of Documentation of Informed Consent ☐Waiver of HIPAA Authorization ☐Waiver/Alteration of Consent Process
Site	☐ Lead Site (For A Multiple Site Research Study) ☐ Data Coordinating Center (DCC)
Research Related Radiation Exposure	☐Yes ☑ No
DSMB / DMC / IDMC	☐Yes ⊠No

OBJECTIVES:

This study aims to examine the impact on epigenetic markers (methylation), gut bacteria, inflammation markers, measures of insulin resistance and patient reported outcomes of well-being in subjects on a 3-day juice-only fast vs calorie restriction vs juice added to regular diet.

BACKGROUND:

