Food is increasingly recognized as a core component of preventive and ameliorative health care. An estimated 90% of cardiovascular disease and diabetes, and 70% of all cancers could be prevented with lifestyle measures. Juice fasting has quickly become one of the most popular self-prescribed dietary interventions in the United States. A wide variety of juice fasts are available in the popular market, the most popular variation is the three-day juice and vegetable fast. According to typical juice fast protocol, the participant is instructed to consume only fruit/vegetable juice for the duration of the fast. The purpose of this study is to assess the efficacy of a 3-d fruit/vegetable juice fast as a dietary intervention with the potential to impact epigenetic markers (methylation), increase beneficial gut bacteria, and improve measures of

insulin resistance leading to improved general well-being.

Dietary interventions utilizing calorie restriction without malnutrition have supported for their ability to extend lifespan through reduction of metabolic rate and oxidative damage and improve markers of age-related diseases such as insulin resistance for diabetes since the 1930s.¹ A 2010 analysis of the mechanism of effect linked fasting to changes in IGF-1, IGFBP1, glucose, and insulin.² A 30% or more decrease in circulating insulin and glucose and decline in IGF-1 can be observed in mammals after 3 days or more of fasting.² Similarly, a 2016 study on 3-day fruit/vegetable juice fasting found significant increases in plasma and urine nitric oxide and a significant decrease in urinary lipid peroxidation.³

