Fruits and vegetables have also been studied for their antioxidant effects due to the phenolic and prebiotic compounds inherent to the foods. The phenolic and micronutrient compounds contribute to the effectiveness of fruits and vegetables as antioxidants. A 2013 study on the effect of increasing fruit and vegetable consumption found increased levels of -tocopherol, lutein, beta carotene, beta cryptoxanthin, and ascorbic acid through diet intervention. Increasing the amount of antioxidants in the diet can combat the effects of oxidative stress which contribute to the development of chronic disease. The beneficial compounds of fruits and vegetables remain obtainable in pressed fruit/vegetable juice. A 2017 study found pure pressed fruit and vegetable juices contained the necessary polyphenols and vitamins found in whole fruits and vegetables to maintain the positive relationship between fruit/vegetable consumption and lower incidence of chronic noncommunicable disease. Similar to studies with whole fruit, participants consuming pure fruit/vegetable juices had lower levels of lipid peroxidation and higher levels of most plasma/serum antioxidant vitamins. Therefore, pressed fruit/vegetable juices are an appropriate method through which to study the effects of fruit/vegetable consumption on the development of chronic disease.

Despite the popularity of 3-day juice fast, there is little existing literature delineating the effects of the diet intervention over other fasting protocols. 3-day juice fast programs qualify as a fast under the definition of fasting due to the low caloric intake of the participant. The 3-day juice fast program we will be utilizing provides approximately 800 -900 kcal per day, 60% and 70% less than the average recommended daily intake for women and men age 19-30, respectively. The purpose of this study is to delineate the mechanism through which juice fasting interventions affect change in methylation, gut microbiome, and inflammation markers.

STUDY ENDPOINTS:

The primary endpoints of the study are changes in epigenetic markers, gut microbiota, and biomarkers of inflammation and insulin resistance that may potentially occur after juice fasting. Secondary goals of the study include providing a foundation for future studies to examine the mechanisms of the intervention and test the intervention in a larger scale.

STUDY INTERVENTIONS / INVESTIGATIONAL AGENTS:

Group 1: Juice Fasting

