At the conclusion of the study, participants will bring back the final biological samples (stool wipe and saliva), provide the fourth bloodspot sample, and be debriefed about the purposes of the study.

The biological samples collected will then be processed and assayed for microbiome, methylation, inflammatory markers, and glycemic markers.

All questionnaire data will be stored in a REDCap database, separate from screening surveys, which are not to be used as study data. REDCap is a secure, web-based application designed to support data collection and management activities for research studies, and these databases will be hosted by the Feinberg School of Medicine.

DATA AND SPECIMEN BANKING:

If fewer participants drop out than anticipated, any excess blood/stool/saliva samples will be banked for later assay. All such specimens will be stored at the Center for Population Epigenetics.

Consent forms and demographic information will be added to Study Tracker, per FSM participant tracking policy.

The specimens will be stored in a -80C freezer at the Center for Population Epigenetics, Northwestern University, located at [name]. The specimen can be accessed through the principal investigators and lab manager.

The procedure to release specimen and data:

- 1. Requester submits application to principal investigators with specific aims and specimen number and list;
- 2. The principal investigators review and approve the request of specimen and related data;
- 3. The request is forwarded to lab manager, who will conduct the sample recording and retrieval from the freezer.
- 4. The data associated with specimens related to the study including patient ID, date of collection, time of collection, and time point, will also be released.

SHARING OF RESULTS WITH PARTICIPANTS:

We have no plans to share individual participants' results. Aggregate data will be available to participants upon request.

STUDY TIMELINES:

Recruitment and data collection will last for three months. Each participant will stay in the study for 21 days (if they choose to complete the study). Primary analyses are expected to be

INCLUSION AND EXCLUSION CRITERIA:

Participants have to meet the all of the following criteria to participate in the study:

- 1. Subjects considered as healthy by the investigator based on medical history and completion of the screening questionnaire.

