Diet intervention: Fasting and juice cleanse diets over short periods are generally safe, but may cause some minor discomfort during the study period. For those on restricted intake diets, several minor adverse effects may occur and include constipation, headache, muscle cramps, diarrhea, general weakness, and rash. Most of these are short-lived, and are generally alleviated by adequate fluid intake and other minor diet modifications. The restricted diet may lead to decreases in glucose levels; this risk will be mitigated by screening participants for the exclusion criteria of diabetes, hypoglycemia, steroid-dependent diseases and use of medications that impact on blood sugar such as sulfonylureas and insulin.

Blood Spot: There is a small risk that the puncture associated with the blood spot may cause bruising or infection at the site of the needle insertion.

Weight, height and waist circumference measurements: There is no physical risk involved in measuring weight, height, and waist circumference but there is a risk of embarrassment or discomfort at being measured in one's underclothes.

Behavioral and psychological questionnaires: These carry a minimal risk for emotional discomfort and stress.

Participants will be fully informed of all of these risks during the informed consent process and be given the opportunity to withdraw from the study at any time without any further obligation. No data will be collected until informed consent has been obtained. We expect all of these risks to be temporary, and to quickly subside after the study is concluded.

Efforts to minimize risk are as follows:

Dietary intervention: Participants will be instructed to speak to the research associate or principal investigator if they experience discomfort, such as constipation, diarrhea, weakness, muscle cramps, or dizziness. There is instruction provided with the juice cleanse on how to address any potential side effects stemming from the diet. Participants will be told that their participation is voluntary and they can choose to withdraw from the study at any time without any further obligation.

Blood spot: Bloodspot collection will be done as professionally and comfortably as possible. Blood is collected for the in-person assessments in a sterile manner to reduce the threat of infection. Likewise, pressure is applied to the puncture site to prevent hemorrhage and ecchymosis.

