One set of de-identified labeled bloodspot samples will be collected in sealed plastic bags and placed with a freeze pack inside of an insulated shipping container. We will seal the box tightly with tape and ship specimens via courier to:

Laboratory for Human Biology Research at Northwestern University Department of Anthropology, [name]; [contact]

Contact: [name]; email: [contact]

No names or individual identities will be used in publications resulting from the study. Physical records will be kept in an area accessible only to research staff. Research data will be stored on a secure, HIPAA-compliant server and drive with monitored and controlled access for study staff and investigators. Survey data will be hosted on secure servers. A key linking study ID to participant names will be kept in a password-protected file on a secure FSM server, separate from study data.

Biomarker Testing

Whole Blood Testing

Inflammatory Stress and Glycemic Biomarkers will include (C-reactive protein, interleukin-6, insulin, leptin). These biomarkers will be assayed using the finger prick/filter paper collection procedure. Blood spot samples will be collected at each scheduled time point in the protocol at the Osher Center for Integrative Medicine clinic or a mutually determined region on the Northwestern campus (in order to accommodate participants' schedules). Throughout all stages of blood collection and processing, Universal Precautions will be followed. Each participant's finger will be cleaned with alcohol and then pricked with a sterile, disposable, widely available micro-lancet commonly used by diabetics. Five drops of whole blood will be collected on standardized filter paper.

Samples will be dried overnight and stored in a -80C freezer at the Northwestern University, Department of Medical Social Sciences, [name] until analysis, at which time specified samples will be transported to the appropriate lab.

Blood spot samples will be analyzed using previously validated ELISA protocols previously developed for use with dried blood spots. Samples will be analyzed for inflammatory and glycemic index markers using a high sensitivity immunoturbidimetric assay on the Hitachi 917 analyzer (Roche Diagnostics—Indianapolis, IN) and the Luminex® 200™ System (Luminex Corporation, Austin, TX), separately. All samples are run in duplicates.

Physiologic Measures

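### Insulin resistance is an aim and a primary endpoint, but the listed blood panel measures insulin and leptin without glucose or a stated fasting state, so it cannot support a conclusion about insulin resistance

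*Protocol*

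**What the plan says.** The Objectives list "measures of insulin resistance and patient reported outcomes of well-being" among the things the three diets are to be compared on. The Background repeats improvement in insulin resistance as part of the study's purpose. Study Endpoints then states: "The primary endpoints of the study are changes in epigenetic markers, gut microbiota, and biomarkers of inflammation and insulin resistance".

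The assays are described in two places. Procedures Involved says only that samples will be "assayed for microbiome, methylation, inflammatory markers, and glycemic markers", with no analyte named. Biomarker Testing, under Whole Blood Testing, gives the list: "Inflammatory Stress and Glycemic Biomarkers will include (C-reactive protein, interleukin-6, insulin, leptin". The same section describes finger-prick drops dried on filter paper, frozen and assayed later. The place of collection may be arranged to suit the participant, and no fasting state is required.

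Glucose levels appear in two places, neither of them an assay. The Background reports: "A 30% or more decrease in circulating insulin and glucose and decline in IGF-1 can be observed in mammals after 3 days or more". Risks to Participants warns: "The restricted diet may lead to decreases in glucose levels". Blood sugar is otherwise mentioned only in connection with excluded conditions and medications.

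**The concern.** Insulin resistance describes how much insulin is present for the glucose it acts on. The protocol expects both quantities to move under restriction and makes the relation between them part of the primary endpoint, but it measures only one of them.

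A lower insulin concentration straight after the restricted days is what the protocol's own Background would lead one to expect from low intake. If that result were presented under the endpoint's present label, a change in concentration could be taken for a change in insulin resistance. A standard fasting state would make insulin a more interpretable crude marker, but the protocol sets none. One named component of the primary endpoint is therefore not delivered by the assays that are meant to deliver it.

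**Working it through.** The protocol gives no figure to reproduce here. The check is a comparison of sections, followed by a short illustration.

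**1. Endpoint against assay.**

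| Place in the protocol | Content |
|---|---|
| Objectives; Background (study purpose); Study Endpoints | Insulin resistance is an aim and part of the primary endpoint |
| Procedures Involved | Glycemic markers, none named |
| Biomarker Testing, Whole Blood Testing | C-reactive protein, interleukin-6, insulin, leptin |
| Background; Risks to Participants | Glucose expected to change; not measured |

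No section names glucose, HbA1c, C-peptide or a derived index as a measurement. Of the four listed analytes, insulin is the only one that bears directly on insulin resistance.

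**2. What an insulin-only reading leaves open.** Inputs: a 30% fall in insulin, the lower bound of the Background's statement for fasting mammals, and an index proportional to insulin x glucose. The index is my assumption and is not in the protocol. The glucose changes are scenarios; only the 30% fall has a source in the Background.

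Index relative to baseline = 0.70 x (1 + change in glucose)

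| Change in glucose | Index relative to baseline | Change in index | Insulin-only reading |
|---|---|---|---|
| -30% | 0.70 x 0.70 = 0.49 | -51% | -30% |
| 0% | 0.70 x 1.00 = 0.70 | -30% | -30% |
| +10% | 0.70 x 1.10 = 0.77 | -23% | -30% |
| +43% (1/0.70 = 1.43) | 1.00 | 0% | -30% |

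The same insulin result fits all four rows.

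**3. What the table also shows.** In the first row, where both quantities fall as the Background describes, the index falls further than insulin alone (51% against 30%). Adding glucose supplies the missing quantity, but it does not by itself separate low intake from improved insulin resistance.

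**4. How far the Background figure carries.** It concerns mammals fasting three days or more. The six juices sum to 140 + 170 + 120 + 130 + 120 + 140 = 820 kcal and 34 + 30 + 28 + 24 + 23 + 36 = 175 g carbohydrate a day. The protocol gives no expected change in insulin at that intake, so the 30% is illustrative and not a prediction for the juice arm.

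**The case against.** **The design already deals with reduced intake.** The caloric-restriction arm is matched to juice fasting at 800-900 kcal a day, so that randomised contrast holds calories roughly equal. Procedures Involved also plans a sample 14 days after the intervention, when low insulin would not simply be the acute effect of three restricted days. Both points stand in part. The matched arm does not help with change from baseline or with comparison against juice plus usual diet, and the two matched diets differ in composition. The later sample still yields an insulin concentration with no glucose and no stated fasting state.

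**The analyte list may not be exhaustive, or the SAP may settle it.** The list is introduced as what the biomarkers will include, but no other section adds glucose. An SAP can define an index; it cannot supply a measurement that was never taken.

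**The endpoint promises biomarkers of insulin resistance, not a glucose-insulin index.** Insulin can be offered as a crude surrogate. That would at least need a controlled prandial state, which the protocol does not state.

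**Stronger readings that a reader might infer.** The documents do not support three of them:
- *The missing glucose is the reason low intake cannot be told from improved insulin resistance.* When both fall, a product index falls further than insulin alone, so glucose would not by itself resolve this.
- *The question cannot be addressed in any arm because less is eaten.* The juice-plus-usual-diet arm has no intake restriction on its intervention days, so that explanation does not carry over to it.
- *A fall in insulin will be reported as improved insulin resistance.* No section says how insulin results will be interpreted.

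**Conclusion.** The point holds as a mismatch between a primary endpoint and its assays. The protocol names insulin resistance as an aim and an endpoint, lists insulin and leptin as the only glycemic analytes, assays glucose nowhere and sets no fasting state. Insulin concentration alone therefore cannot support a conclusion about insulin resistance, and the calorie-matched arm and 14-day sample only partly offset this.

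On the assumed product index, one and the same 30% fall in insulin is compatible with anything from a 51% fall to no change, depending on an unmeasured quantity. The range rests on that index and on chosen glucose scenarios, so it shows the ambiguity and does not estimate a bias. The absence of glucose and of a fasting requirement rests on the protocol text alone. The defect affects one component of a multi-part primary endpoint and leaves the methylation, microbiome and inflammation components untouched. It should be corrected, and correcting it changes what the trial may claim.

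**What to change.** In the Objectives, in the Background's statement of the study's purpose and in Study Endpoints, replace insulin resistance with insulin and leptin concentrations. Add a sentence that no conclusion on insulin resistance will be drawn from them. This costs protocol wording only, with no change to visits, samples or assays; the downside is a more modest claim.

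If the sponsor prefers to keep the insulin-resistance endpoint, three additions are needed together:
- a glucose measurement at the same four visits, at most 30 participants x 4 = 120 readings;
- a standard prandial state for every blood sample;
- a named index that combines insulin and glucose.

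This is not a free extra reading. The protocol describes only dried filter-paper spots and names no glucose device or dried-spot glucose assay, so a new device or assay with its own procedure and supplies would have to be added. The protocol should also say that a fall in the index right after the restricted days will not by itself be read as improved insulin resistance.
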